9.4.2 ANALYSIS OF THE PRIMARY ENDPOINT(S)

Details of the analysis of the primary endpoints will be provided in the SAP. A summary of the planned steps are provided here.

The first step will test whether the intervention is associated with differences across groups in the primary oral hygiene clinical outcomes. We will use linear mixed models for continuous outcomes (e.g., plaque index and gingival index) accounting for within-participant correlation over time. In addition to group, all models will be adjusted for site and time point and the interaction between group and time point – to assess whether group difference varied over time – as fixed effects; we will include a random effect for participants to handle within-participant clustering. Significant interaction between group and time point ($p < 0.05$) will provide statistical evidence for the efficacy of the intervention in improving oral health outcomes in Treatment Group 2 as compared to Treatment Group1 and the Control Group.

The subsequent steps will test the strength of the indirect effect of the intervention on oral hygiene clinical outcomes through mediators such as care partner factors and oral hygiene behavior outcomes. The following step will test the indirect effects are stronger than the direct intervention effects in Treatment Group 2 compared with Treatment Group 1 and the Control Group. The final step will test whether the impact of the intervention on oral hygiene clinical outcomes is sequentially mediated first by care partner's factors and then by oral hygiene behavioral outcomes.

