*Target accrual: 120 dyads

Study Design

This is a three parallel arm randomized controlled trial (RCT) to evaluate the effectiveness of a care partner-assisted intervention to improve oral hygiene in individuals (≥ 60 years) with mild dementia. Participant-care-partner dyads were randomized into 1 of 3 groups: Treatment Group 1 (**TG1**), Treatment Group 2 (**TG2**), and the Control Group (**CG**) stratified by site. **TG1** and **TG2** were given smart electronic toothbrushes. Only **TG2** will receive in-home and telephone coaching throughout the duration of the study and were instructed to record daily brushing habits. The coaching sessions included individualized instruction on oral hygiene technique, cueing strategy development, or oral hygiene monitoring and coaching. **TG1** and **CG** did not receive coaching sessions. While randomization occurred at the dyad level (participant-care partner), primary study outcomes will be assessed at the participant level. The study duration was 6 months, including a 3 month intervention phase, in which coaching and educational modules were delivered, followed by a 3 month maintenance phase in which no coaching or educational modules were presented to participants. Data was collected by the study team at three visits: baseline, 3-months (end of active intervention phase), and 6-months (end of three-month maintenance phase). The primary endpoint is oral hygiene (plaque index, gingival index) at 3 months, with a secondary endpoint of 6 months to explore maintenance of intervention effects.

Study Aims

Aim 1: Evaluate the effectiveness of a care partner-assisted intervention to improve oral hygiene and oral hygiene behaviors in individuals with mild dementia.

Hypothesis 1a: Compared to CG, both T1 and T2 will result in improved oral hygiene as measured by reduced plaque index, and reduced gingival index, at 3 months.

Hypothesis 1b: T2 will have higher improvement than T1, relative to CG, in oral hygiene as measured by a greater reduction in plaque index, and gingival index, at 3 months.

Aim 2: Assess changes in mediating factors/process outcomes, including communication between the dyads, oral health knowledge, and self-efficacy for both participants and care partners to understand mechanisms of the intervention.

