General Approach: The overall goal of this study is to demonstrate the effectiveness of the two intervention strategies (TG1, TG2) against that of CG. The primary outcomes are plaque index, which is quantified as the proportion of sites with plaque deposits on at least less than 1/3 of crown, and gingival index, which is quantified as the proportion of sites with at least some mild inflammation. While the unit of randomization is at the dyad level, the primary outcomes will be evaluated at the individual level. As participants and care-partners contribute repeated measures (at baseline, 3 months and 6 months), we will use a linear mixed modeling approach for the analysis of the primary hypotheses, to account for correlation among repeated measures from the same individual. Analyses for all study outcomes will be conducted according to the intention-to-treat (ITT) principle, where all participants are analyzed according to the group in which they were randomized, irrespective of their receipt of allocated treatment. For our primary analysis we will conduct a

complete case analysis, thus excluding participants who are lost to follow up. As a sensitivity analysis, we will use the strategy of last-observation-carried-forward (LOCF) (thus assuming no change), to impute missing values for participants lost to follow up, if a monotone pattern is demonstrated in complete data. A strategy of LOCF is conservative in that it may bias results towards a null effect, but eliminates bias related to differential dropout, especially in the case where participants with no improvement are less likely to complete follow-up assessments. Statistical analyses will be performed in R version 4.4.0. All statistical tests will be two-sided, and a p-value of < 0.05 will be considered statistically significant.

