Statistical Analyses (Aim 1): To examine between-group differences in baseline characteristics and outcome variables, we will use Chi-square tests or Fisher's exact tests to analyze categorical variables and a one-way analysis of variance (ANOVA) for continuous variables. The effectiveness hypotheses will be analyzed using a linear mixed modeling framework with random effects. Specifically, longitudinal outcomes (e.g. plaque index) will be regressed on a treatment indicator, timepoint indicator, interaction of the two, and additional participant-specific covariates as needed. That is for the i^{th} person and t timepoint, $\text{Plaque}_{it} = \alpha_i + \beta_0 + \beta_1 \cdot \text{Site}_i + \beta_2 \cdot X_i + \beta_g \cdot \text{Group}_i + \beta_t \cdot \text{Time}_t + \beta_{gt} \cdot \text{Group}_i \times \text{Time}_t + \varepsilon_{it}$, where the terms represent the following: α_i person-specific random effects, β_0 overall mean plaque, β_1 site effects, X_i additional participant-specific covariates, β_g group effects, β_t time effects, and β_{gt} the interaction effect between group and time. Covariates determined a priori (including: baseline index scores, baseline functional status) will be included via the flexible X_i term. If data suggest a between-group difference (e.g. significant interaction between time and group) on the primary outcomes of interest, we will conduct the following pairwise comparisons using estimated means (**TG1 vs. CG**; **TG2 vs. CG**), at 3 months and 6 months. To control for multiple comparisons, pairwise comparisons will incorporate a False Discovery Rate-controlling procedure (e.g. Benjamini-Hochberg) which yields the desired type-I error rate of 5%. Lastly, depending on the distribution of the proportions for the primary outcomes (plaque, gingival indices) we may explore alternative distributions (e.g. beta regression) if it improves model fit. To address secondary outcomes including: 1) participants' frequency of toothbrushing, 2) participant's duration of toothbrushing, 3) participants frequency of interdental cleaning, 4) participant's interproximal cleaning technique, and 5) participants' oral hygiene skills score, and 6) participants' oral health knowledge score, we will use the same analytic approach outlined above consisting of linear mixed modeling with random effects. Given the overall sample size and number of secondary outcomes, all secondary outcome analyses will incorporate an appropriate False Discovery Rate-controlling procedure (e.g. Benjamini-Hochberg).

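### The primary mixed model uses the baseline index both as a response and as a covariate, so the standard errors of its 3- and 6-month treatment contrasts are too small

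*Combined protocol and SAP*

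**What the plan says.** The SAP, General Approach, sets the response rows: "As participants and care-partners contribute repeated measures (at baseline, 3 months and 6 months), we will use a linear mixed modeling approach". Under Statistical Analyses (Aim 1), each outcome "will be regressed on a treatment indicator, timepoint indicator, interaction of the two, and additional participant-specific covariates as needed". The equation there has a person-specific random effect, one residual term and a single time-constant coefficient on the covariate vector X_i. The covariates are then named: "Covariates determined a priori (including: baseline index scores, baseline functional status) will be included". Nothing removes the baseline row when the baseline index is a covariate.

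Contrasts follow a gate: "If data suggest a between-group difference (e.g. significant interaction between time and group) on the primary outcomes of interest". If it opens, TG1 and TG2 are each compared with CG on estimated means at 3 and 6 months, and "pairwise comparisons will incorporate a False Discovery Rate-controlling procedure (e.g. Benjamini-Hochberg) which yields the desired type-I error rate of 5" percent. SAP, Study Design, fixes the primary time point: "The primary endpoint is oral hygiene (plaque index, gingival index) at 3 months".

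Protocol 9.4.2 describes the model without a baseline covariate: "In addition to group, all models will be adjusted for site and time point and the interaction between group and time point", and "we will include a random effect for participants to handle within-participant clustering".

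**The concern.** On the baseline row the response equals one of its own predictors, so the baseline slope that fits that row perfectly is 1. On the follow-up rows the right slope is the correlation with baseline. The model allows only one slope, so it fits an average of the three. It also pools into one random-intercept variance and one residual variance a row that has no variation left given the covariate and rows that do. The adjusted contrasts at 3 and 6 months then use the wrong slope and a variance estimate that is too small.

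Those contrasts, at 3 months, are the primary comparisons for both plaque and gingival index. Their confidence intervals would be too narrow, and neither the interaction gate nor Benjamini-Hochberg (BH) widens an interval. Hypothesis 1a claims a benefit for both treatment groups, so each arm's contrast has to be trustworthy when the other arm works.

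**Working it through.** The plan gives no standard error, between-visit correlation or error rate for this model, so there is no figure of its own to reproduce. Correlations and effect sizes below are assumptions.

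**Inputs from the documents.** Visits at baseline, 3 and 6 months; random intercept; baseline index in X_i; complete-case analysis, so every person has all three rows; two-sided 5%; completers TG1 18, TG2 17, CG 19 (table of sample size as of 05/08/24).

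**Closed form.** Take unit variance at each visit. Let ρ0t be the correlation of visit t with baseline, and ρ̄ the mean of the three pairwise correlations.

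- Fitted baseline slope: b = (1 + ρ03 + ρ06)/3.
- Variance the model reports for an adjusted mean (per arm, times n): [Var(Ȳ) − b²] + (2/3)(1 − ρ̄).
- True variance of that adjusted mean: 1 + b² − 2bρ0t.

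With equal correlation r these reduce to (1−r)(8+4r)/9 and (1−r)(10+8r)/9. The ratio of reported to true standard error is √[(4+2r)/(5+4r)], the same at both follow-up visits.

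| Equal correlation r | 0.3 | 0.5 | 0.7 |
|---|---|---|---|
| Fitted slope b (should be r) | 0.53 | 0.67 | 0.80 |
| Reported variance | 0.716 | 0.556 | 0.360 |
| True variance | 0.964 | 0.778 | 0.520 |
| SE ratio | 0.861 | 0.845 | 0.832 |
| SE too small by | 13.9% | 15.5% | 16.8% |

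With decaying correlation (r between adjacent visits, r² between baseline and 6 months), take r = 0.5. Then b = (1 + 0.5 + 0.25)/3 = 0.583 and the reported variance is 0.271 + 0.389 = 0.660. The true variance is 0.757 at month 3 and 1.049 at month 6. The ratios are √(0.660/0.757) = 0.934 and √(0.660/1.049) = 0.793.

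| Decay, adjacent r | 0.3 | 0.5 | 0.7 | 0.8 |
|---|---|---|---|---|
| Month-3 SE too small by | 8.4% | 6.6% | 4.4% | 3.1% |
| Month-6 SE too small by | 16.7% | 20.7% | 24.4% | 26.1% |

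**Simulation of the SAP model.** REML random-intercept fit; arms 18/17/19; site, functional status (correlation 0.3 with baseline assumed) and baseline index in X_i; Satterthwaite degrees of freedom; interaction F gate; BH over the four contrasts; 20,000 replicates. The fit agrees with a general mixed-model routine to four decimals.

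| Month 3, equal correlation | 0.3 | 0.5 | 0.7 |
|---|---|---|---|
| Model SE / true SD | 0.86 | 0.84 | 0.82 |
| 95% interval coverage | 90.8% | 90.3% | 89.4% |
| Unadjusted 5% test, error | 9.1% | 9.7% | 10.6% |
| Gate + BH: TG2 null, TG1 effect 1 SD | 6.4% | 8.0% | 8.7% |
| Same, baseline index not a covariate | 3.2% | 3.4% | 3.6% |
| Gate + BH: TG2 null, TG1 effect 0.5 SD | 3.1% | 4.1% | 5.7% |
| Same, baseline index not a covariate | 1.1% | 1.3% | 1.6% |

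Under decay with adjacent correlation 0.5 to 0.8, unadjusted error is 5.8 to 6.8% at month 3 and 11.7 to 15.0% at month 6, where interval coverage is 85 to 88%. With gate and BH and a 1 SD effect in the other arm, month-6 error for the null arm is 9.2 to 12.2%, against 3.4 to 3.7% without the covariate. Skewed proportions (beta marginals, correlation 0.5, 6,000 replicates) give 9.1 to 9.6% unadjusted error at month 3.

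**What is not affected.** The interaction gate rejects at about 5 to 6% when no arm works. In that case gate and BH together leave 1.4 to 1.7% error on the month-3 contrast. A contrast of changes from baseline has 4.9 to 5.3% error under equal correlation, because the time-constant baseline term cancels.

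**The other reading.** If only 3 and 6 months are responses, the group-by-time term tests only whether the effect changes between those visits. With a sustained 0.8 SD benefit in both arms, an interaction gate opens in 5% of trials and a group main-effect gate in 91 to 98%.

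**The case against.** The arithmetic is not in dispute; its weight is.

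- **The procedure absorbs much of the error.** The SAP does not plan unadjusted 5% tests, and BH controls the false discovery rate. This stands for declarations: with one arm effective by 1 SD, that rate is 4.6 to 5.4% under equal correlation, near nominal, though about double the 2.3 to 2.5% without the covariate. It does not help the intervals.
- **The larger error rates need a large effect in one arm only.** At 0.3 SD the gated month-3 error is 2.0/2.5/3.0% for equal correlation 0.3/0.5/0.7. Protocol 9.2 gives an effect size of 0.3 without a metric. Read as Cohen's f with one effective arm, it is 0.3/(√2/3) ≈ 0.64 SD, and the error is 4.2/5.6/7.4%, against about 1.5 to 2% without the covariate. This limits the size of the testing problem.
- **Under decaying correlation the primary time point is nearly unharmed.** Gated month-3 error at 1 SD is 4.7 to 4.9% (adjacent correlation 0.5 and 0.7), and month 6 is secondary. This stands as well: the shortfall at month 3 runs from about 3 to 18% depending on an unknown correlation.
- **The text might be read as 3 and 6 months only.** The equation does not list its time points and X_i is described as flexible. But General Approach names baseline as a repeated measure, and the alternative reading brings its own fault in the gate. The ambiguity is a further reason to decide.
- **The protocol left covariates to the SAP** (Protocol 9.4.1), and the SAP lists no TG2-TG1 contrast, so Hypothesis 1b is not directly affected. Both are fair. Neither makes the double use valid.

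**Conclusion.** The concern holds. As written, the SAP puts the baseline index on both sides of the primary model, and the standard errors of the TG1-CG and TG2-CG estimated-mean contrasts are understated. Under equal visit correlation of 0.3 to 0.7 the shortfall is about 14 to 18% at both follow-up visits. Under decay it is small at month 3 and about a fifth to a quarter at month 6. The stated 5% error rate is met when no arm works. Under equal correlation it can be exceeded for an ineffective arm when the other arm is clearly effective.

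The size rests on assumed correlations, equal variances across visits and a random-intercept covariance; the direction held in every scenario examined for the follow-up contrasts. Because the primary intervals are affected and the correction is simple, it should be made before the primary model is run.

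**What to change.** State one of the following in the SAP model paragraph.

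(a) Keep baseline, 3 and 6 months as responses, remove the baseline index from X_i, and constrain the arms to a common baseline mean.

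(b) Use 3 and 6 months as responses with the baseline index as a covariate with a visit-specific slope, and replace the interaction gate with a test of the group effect at 3 months.

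Use an unstructured visit covariance in either case. With only a random intercept and decaying correlation of 0.6 to 0.8, month-6 error stays at about 8 to 9% under (a) and 7 to 8% under (b). A separate ANCOVA at each visit is a simple alternative or check; it gave 4.9 to 5.2% in every normal-data scenario.

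Merely deleting the baseline index, which returns to the protocol's model, restores nominal error under equal correlation (4.7 to 5.4% unadjusted). It gives up the precision of baseline adjustment in the estimated means: per-arm variance 1 instead of 1 − r², or 0.75 at r = 0.5.

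The cost is one or two sentences and no new data. Reported standard errors become larger, and correct. The unstructured covariance estimates a few more variance parameters from about 54 completers.

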9 STATISTICAL CONSIDERATIONS

9.1 STATISTICAL HYPOTHESES

Primary Efficacy Endpoint(s):

- H1 (Objective 1): There will be an improvement in the oral hygiene clinical outcomes (lower plaque index and lower gingival index) from baseline to Month 3 and Month 6, and from Month 3 to Month 6. Treatment Group 1 will have a higher rate of improvement than the control group while Treatment Group 2 will have the highest rate of improvement.
- H2b (Objective 2b): The effects of the intervention on oral hygiene clinical outcomes (i.e., plaque index and gingival index) will be mediated by a set of mediating variables controlling for selected key covariates.
- H3a (Objective 3a): The effects of the intervention on oral hygiene clinical outcomes (i.e., plaque index and gingival index) will be mediated by oral hygiene behavioral outcomes controlling for selected key covariates.
- H3b (Objective 3b): The effects of the intervention on oral hygiene clinical outcomes (i.e., plaque index and gingival index) will be mediated by care partner's factors, and then mediated by oral hygiene behavioral outcomes controlling for selected key covariates.

Secondary Efficacy Endpoint(s):

- H1 (Objective 1): There will be an improvement in the oral hygiene behaviors (better oral hygiene skills and higher frequency of toothbrushing) from baseline to Month 3 and Month 6, and from Month 3 to Month 6. Treatment Group 1 will have a higher rate of improvement than the control group while Treatment Group 2 will have the highest rate of improvement.
- H1 (Objective 1): There will be an improvement in the oral hygiene behaviors (longer duration of toothbrushing) from the first week of the intervention (average in Week 1) to Month 3 (average in Month 3) and Month 6 (average in Month 6), and from Month 3 to Month 6. Treatment Group 2 will have longer duration of toothbrushing than the Treatment Group 1.
- H2a (Objective 2a): The effects of the intervention on oral hygiene behavioral outcomes (i.e., the duration and frequency of toothbrushing and oral hygiene skills) will be mediated by a set of mediating variables controlling for selected key covariates.

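### SAP Hypothesis 1b (TG2 better than TG1 at 3 months) has no named contrast or interval, and the protocol reads a three-arm interaction in its place

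*Combined protocol and SAP*

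**What the plan says.** - **Hypothesis.** SAP, Study Aims, Hypothesis 1b: "T2 will have higher improvement than T1, relative to CG, in oral hygiene", measured by plaque and gingival index at 3 months. Protocol 9.1 expects the same ordering: TG1 should improve more than control, "while Treatment Group 2 will have the highest rate of improvement".
- **Planned contrasts.** SAP, Statistical Analyses (Aim 1), fits a mixed model with group, time and their interaction. The pairwise step is conditional: "If data suggest a between-group difference (e.g. significant interaction between time and group"). It then lists "pairwise comparisons using estimated means (TG1 vs. CG; TG2 vs. CG), at 3 months and 6 months". On multiplicity, "pairwise comparisons will incorporate a False Discovery Rate-controlling procedure (e.g. Benjamini-Hochberg").
- **Stated goal.** SAP, General Approach: to "demonstrate the effectiveness of the two intervention strategies (TG1, TG2) against that of CG".
- **Protocol rule.** Section 9.4.2 treats a significant group-by-time interaction as evidence for the intervention in "improving oral health outcomes in Treatment Group 2 as compared to Treatment Group1 and the Control Group". Section 9.4.3 repeats this for the behavioural outcomes. Section 9.4.2 also says that "Details of the analysis of the primary endpoints will be provided in the SAP".
- **Elsewhere in the SAP.** The fallback effect sizes for the mediators use the same two control contrasts. No section plans a TG2 versus TG1 test or interval for plaque or gingival index.

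**The concern.** TG1 versus control shows what the smart toothbrush adds to the booklet. Only TG2 versus TG1 shows what the rest of the TG2 package adds to toothbrush and booklet. Protocol 4.2 makes this question central: both of these arms improved in the pilot, and the control group was added because the brush itself may be active.

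As written, a hypothesis on the primary outcomes at the primary time point has no analysis assigned to it. The one decision rule that the documents attach to TG2 over TG1 is the three-arm interaction. That test can be significant because both treatment arms differ from control, with no difference between them. A reader who applies the protocol's rule could therefore credit the coaching package with a benefit that the data do not show. The same mistake can arise if TG2 is significant against control and TG1 narrowly is not.

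**Working it through.** **Inputs from the documents.** Completers: control 19, TG1 18, TG2 17 (SAP, sample size as of 05/08/24). Two-sided 0.05 and complete-case primary analysis (SAP, General Approach). Effect size 0.3, metric not named, with 107 subjects for 80% power (protocol 9.2).

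**Assumptions, because the documents give no values.** Effects in SD units, equal at 3 and 6 months; compound symmetry with correlation ρ = 0.5 (range 0.3 to 0.7); the SAP's gate read as a group-by-time F test at p < 0.05. The SAP offers that test only as an example, so this is one reading.

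**1. The plan's own sample size.** With 0.3 read as Cohen's f in a three-group, 2-df omnibus test, the required N is 108, and power at 107 is 79.98%. With 0.3 read as a two-group difference in SD, 175 per arm are needed. The figure of 107 therefore matches an omnibus comparison and not TG2 versus TG1.

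**2. What 1b is.** (TG2 − CG) − (TG1 − CG) = TG2 − TG1. The phrase about control in 1b changes nothing.

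**3. The interaction when TG1 = TG2.** Let both treatment arms follow (0, d, d) over the three visits and control (0, 0, 0).
- Centred on its mean, the treated profile is (−2d/3, d/3, d/3), with sum of squares 2d²/3.
- With 35 treated and 19 control, λ = (35 × 19 / 54) × (2/3) × d² / (1 − ρ) = 12.315 × 0.667 × d² / 0.5 = 16.42 d².
- Degrees of freedom are 4 and (54 − 3) × 2 = 102; the critical F is 2.46.

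| d (SD) | λ | P(interaction significant) |
|---|---|---|
| 0.3 | 1.5 | 13% |
| 0.5 | 4.1 | 31% |
| 0.735 | 8.9 | 63% |

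Simulation gives 13.0%, 31.0% and 63.0%. Over d from 0.3 to 0.8 and ρ from 0.3 to 0.7 the range is 10% to 92%. A direct TG2 versus TG1 test at 3 months (ANCOVA on baseline) rejects in 4.8% to 5.5% throughout.

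**4. Comparing the two control verdicts.** In simulation with TG1 = TG2, ρ = 0.5 and d from 0.5 to 0.8, TG2 is significant against control while TG1 is not in 11–16% of trials unadjusted, 9–11% after Benjamini-Hochberg, and 4–6% after Benjamini-Hochberg and the gate.

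**5. Which model supplies the contrast.** The SAP lists baseline among the repeated outcome measures and also names baseline index scores as a covariate. Read literally, baseline is used twice. At ρ = 0.5 the sampling SD of the adjusted contrast is about 0.338 × √(1 − 0.25) = 0.29 SD, and simulation of the literal model agrees. The SE that this model reports averages about 0.25. The nominal 5% test of TG2 versus TG1 then rejects in about 8–10% of trials when the arms are equal. ANCOVA stays near 5%.

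**6. Precision of the direct contrast.** SE = √(1/17 + 1/18) = 0.338 SD. Unadjusted 95% half-width = 2.035 × 0.338 = 0.69 SD. With baseline adjustment at ρ = 0.5 it is 0.69 × 0.866 = 0.60 SD. Unadjusted power is about 14%, 30% and 63% at 0.3, 0.5 and 0.8 SD.

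**The case against.** The strongest defence is that the SAP's stated goal is each strategy against control, so the two listed contrasts are the ones intended. On this view a contrast with 14% power at 0.3 SD adds little, and the control comparisons are sound without it. This explains the omission and limits its weight: neither the data nor the control contrasts are in question. It does not remove Hypothesis 1b, and low power is a reason to show the interval.

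Three stronger readings are tempting, and the documents do not support them.
- A reader might infer that TG2 minus TG1 is unavailable unless the gate opens. The mixed model is fitted before the gate, and its terms fix this contrast and its SE in every trial. The gate governs only the listed comparisons.
- A reader might infer that any TG2 versus TG1 result would be purely post hoc. Hypothesis 1b already states the arms, direction, outcomes and time point. What is unspecified is the analysis. Nor is the protocol silent: it has a rule, but an invalid one.
- A reader might infer that the plan would build the interval by combining the two control intervals as if independent. No section proposes this.

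It is also fair to say that the larger percentages depend on assumed effects. At 0.3 SD, the only effect size in the documents, the interaction figure is 13%. That is still more than twice the nominal 5%.

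**Conclusion.** The concern holds as a gap in specification together with an invalid decision rule. Hypothesis 1b is TG2 minus TG1. The SAP names no such contrast, test or interval, although its model yields one, and protocol 9.4.2 and 9.4.3 substitute an omnibus interaction that cannot distinguish the two treatment arms. If TG1 and TG2 are equal, that rule would point to TG2 over TG1 in about 13%, 31% and 63% of trials at 0.3, 0.5 and 0.735 SD, against about 5% for a valid direct test. These figures assume ρ = 0.5, compound symmetry, equal effects at both follow-up visits and one reading of the gate. That the rule is invalid does not depend on them.

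This should be fixed, preferably before comparative results are seen. It does not undermine the comparisons with control.

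**What to change.** 1. **SAP, Aim 1.** Name TG2 versus TG1 at 3 months, with 6 months supportive, as the analysis of Hypothesis 1b for both indices. Report the estimate and 95% CI whether or not the gate opens. Include the contrast in the false-discovery-rate procedure, and claim significance only if the gate opens and it passes.
2. **Model.** Use baseline once: either as a covariate for the 3- and 6-month outcomes or as an outcome row, not both.
3. **Protocol 9.4.2, and 9.4.3 for outcomes measured in all three arms.** Replace the TG2-over-TG1 reading of the interaction with a reference to this contrast. State that a significant TG2 versus control beside a non-significant TG1 versus control is not evidence for 1b.
4. **Interpretation.** State that precision is low, so a non-significant result does not show that the TG2 package adds nothing.

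If the sponsor does not intend to test 1b, relabel it as exploratory and still report the estimate and CI.

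**Cost.** Wording, and one more contrast per outcome and time point; no new data. The contrasts go from 2 × 2 × 2 = 8 to 3 × 2 × 2 = 12 over both outcomes and both time points. In one assumed ANCOVA scenario (TG1 0.37 SD, TG2 0.735 SD, ρ = 0.5, gate applied, one family per outcome and time point), power falls by about 2 points for each control contrast: from 38% to 36% for TG2 and from 16% to 14% for TG1. Using baseline once also gives up the apparent precision of the literal model, which was not real.
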